## 9.4 **Populations for Analyses**

- The Safety (SA) population will include all subjects who received study influenza challenge.
- The Intent-to-Treat (ITT) population will consist of all subjects who received study influenza challenge.
- The Per-Protocol (PP) population will include subjects in the ITT population with the following exclusions of data:
  - All data from any subjects who withdraw prior to the end of the challenge period
  - Data from any visit that occurs substantially out of window

- Data from all visits subsequent to major protocol deviations that could impact the validity of later data, such as:
  - Receipt of immunosuppression or any medications that may be associated with impaired responsiveness
  - Receipt of any investigational drug/investigational vaccine/licensed vaccine
  - Receipt of blood or blood products, or blood donation

Certain analyses may be done on subsets of these populations, such as infected subjects, or those receiving what is determined to be the optimal dose.

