Solicited influenza symptoms will be presented by the frequency and percentage of subjects reporting each symptom, severity, day, and challenge dose group. The self-reported (FLU-PRO) and investigator-assessed symptoms will be tabulated separately. Total symptom scores will be computed for each subject and each scoring algorithm. Mean scores for both algorithms will be calculated for each group, along with 95% CI, and the groups will be compared as described in Section 9.5.1. Additionally, the number and percentage of subjects meeting each scale's definition of symptomatic and asymptomatic will be cross-tabulated by challenge dose group. A Wilcoxon rank-sum test will be used to compare the distributions of each set of scores, across all subjects that received active challenge, to determine the agreement between the two symptom reporting methods.

Clinical endpoints (including the primary endpoints) will be assessed in the ITT population. Subjects who withdraw during the challenge period prior to meeting discharge criteria will be included in summaries where data are available. Subjects who withdraw during the challenge period and have yet to meet the relevant clinical case definition will be excluded from analyses of aggregate endpoints such as the incidence of symptomatic influenza.

If at least 10% of the analysis data would be dropped according to PP population exclusions described in Section 9.4, the PP population will be used as a sensitivity analysis for the primary ITT analysis.

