5. GENERAL STATISTICAL CONSIDERATIONS

5.1. General Principles

The challenge period is defined as the day of study challenge (Day 1) through discharge from the confinement period (Day 8 or later).

Continuous variables will generally be summarized using the following descriptive statistics: non-missing sample size (denoted by “n”), mean or geometric mean, standard deviation, minimum, median, and maximum. Titers will be summarized with geometric means, first across replicates to compute one value for each individual sample and then across participants within clinical outcome groups. The frequencies and percentages (based on the non-missing sample size) of observed levels will be reported for categorical measures. Data listings will typically be sorted by site or other grouping variable (e.g. infection status), participant, and by visit number within participant, where appropriate. All tables will be annotated with the total population size relevant to that table, including any missing observations.

For continuous variables, confidence intervals will be computed based on the t-distribution, unless the data appear especially non-normal and the sample sizes for the analysis are insufficient to apply the central limit theorem. Bootstrap confidence intervals may be calculated instead if the t-distribution is determined to be unsuitable. For binary variables, confidence intervals will be computed using the exact Clopper-Pearson method.

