5.5. Missing Data and Outliers

All attempts are made to collect all data per protocol, and missing data are expected to be minimal due to the nature of the study, with participants in confinement units for much of the follow-up period. No imputation is planned for missing data.

Any data point that appears to be erroneous or inexplicable based on the observed data distribution and the statistical team's understanding of the analysis variables will be investigated as a possible outlier. If data points are identified as outliers, sensitivity analyses may be performed to examine the impact of including or excluding the outliers. Any substantive differences in these analyses will be reported.

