7. CLINICAL EVALUATIONS

Analysis of clinical endpoints that do not involve immunoassays will be done in the Safety population. Analyses involving immune responses will be conducted using the ITT population. If at least 10% of analysis data would be excluded by the reasons given in [Section 5.3.3](#), some analyses may be conducted in the PP population as well, as a sensitivity analysis.

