Cumulative MJS ≥ 10 across Days 2 through 6, Days 3 through 7, or Days 4 through 8	n (%)	x (x.x)	(x.x, x.x)	x (x.x)	(x.x, x.x)	x (x.x)	(x.x, x.x)	x (x.x)	(x.x, x.x)
Symptomatic Influenza Infection: Viral shedding (by qualitative and/or quantitative RT-PCR) on at least two days and cumulative MJS ≥ 10 across Days 2 through 6, Days 3 through 7, or Days 4 through 8	n (%)	x (x.x)	(x.x, x.x)	x (x.x)	(x.x, x.x)	x (x.x)	(x.x, x.x)	x (x.x)	(x.x, x.x)
Cumulative MJS ≥ 15 across Days 2 through 6, Days 3 through 7, or Days 4 through 8	n (%)	x (x.x)	(x.x, x.x)	x (x.x)	(x.x, x.x)	x (x.x)	(x.x, x.x)	x (x.x)	(x.x, x.x)
Symptomatic Influenza Infection: Viral shedding (by qualitative and/or quantitative RT-PCR) on at least two days and cumulative MJS ≥ 15 across Days 2 through 6, Days 3 through 7, or Days 4 through 8	n (%)	x (x.x)	(x.x, x.x)	x (x.x)	(x.x, x.x)	x (x.x)	(x.x, x.x)	x (x.x)	(x.x, x.x)
Sensitivity Analysis – Varying the Number of Days of Viral Shedding									
Symptomatic Influenza Infection: Viral shedding (by qualitative and/or quantitative RT-PCR) on at least one day and cumulative MJS ≥ 6 across Days 2 through 6, Days 3 through 7, or Days 4 through 8	n (%)	x (x.x)	(x.x, x.x)	x (x.x)	(x.x, x.x)	x (x.x)	(x.x, x.x)	x (x.x)	(x.x, x.x)
Symptomatic Influenza Infection: Viral shedding (by qualitative and/or quantitative RT-PCR) on at least three days and cumulative MJS ≥ 6 across Days 2 through 6, Days 3 through 7, or Days 4 through 8	n (%)	x (x.x)	(x.x, x.x)	x (x.x)	(x.x, x.x)	x (x.x)	(x.x, x.x)	x (x.x)	(x.x, x.x)

Notes: N = Number of participants in the Safety population, n = Number of participants meeting the given criteria during the challenge period. Confidence intervals for the probability of meeting the given criteria computed via the exact Clopper-Pearson method. Confidence intervals for the mean computed via the t-distribution. MJS = Modified Jackson Score.

Table 15: Maximum Severity of Influenza Symptoms Reported During the Challenge Period by Challenge Dose Group, Safety Population

Symptom	Maximum Severity	10 ⁴ TCID ₅₀ Challenge Virus (N=X)		10 ⁵ TCID ₅₀ Challenge Virus (N=X)		10 ⁶ TCID ₅₀ Challenge Virus (N=X)		Sham Inoculum (N=X)	
		n (%)	95% CI	n (%)	95% CI	n (%)	95% CI	n (%)	95% CI
Any Symptom	Any Severity	x (x.x)	(x.x, x.x)	x (x.x)	(x.x, x.x)	x (x.x)	(x.x, x.x)	x (x.x)	(x.x, x.x)
	None	x (x.x)	-	x (x.x)	-	x (x.x)	-	x (x.x)	-
	Mild or Just Noticeable	x (x.x)	-	x (x.x)	-	x (x.x)	-	x (x.x)	-

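### Protocol 9.5.2 drops only withdrawals who are not yet cases, so the attack-rate denominator depends on the outcome, and the SAP neither adopts nor replaces the rule

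*Protocol*

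**What the plan says.** Protocol 9.5.2 fixes the population for the AR: "Clinical endpoints (including the primary endpoints) will be assessed in the ITT population". Protocol 9.4 defines it: "The Intent-to-Treat (ITT) population will consist of all subjects who received study influenza challenge". Protocol 9.5.2 then adds an exception for early leavers: "Subjects who withdraw during the challenge period and have yet to meet the relevant clinical case definition will be excluded from analyses of aggregate endpoints". It names the incidence of symptomatic influenza as an example of such an endpoint. A subject who leaves after meeting the definition is not covered by the exception and stays in both numerator and denominator.

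The SAP does not mention this exception. Its section 7 moves the analysis: "Analysis of clinical endpoints that do not involve immunoassays will be done in the Safety population". The footnote to the primary results table, Table 14, reads: "N = Number of participants in the Safety population, n = Number of participants meeting the given criteria during the challenge period". SAP 5.1 sets the general rule for percentages: "The frequencies and percentages (based on the non-missing sample size) of observed levels will be reported for categorical measures". The same section lets the N printed on a table include subjects with missing observations. SAP 5.5 adds: "No imputation is planned for missing data". SAP section 14 reports no substantive departure from the protocol's planned analysis.

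**The concern.** Whether a subject counts in the primary denominator should not depend on whether that subject has already had the event. The case definition needs shedding on two days from Day 2 and a symptom score of 6 within a five-day window, so it can be met before Day 8. Of two subjects who leave on the same day, the one already classed as a case is kept and the other is removed.

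The AR chooses the dose. Under protocol 9.5.2 the optimal dose is the safe group with the highest estimated AR, and final group sizes are given as roughly 10 to 30. One or two subjects more or fewer in the denominator move the estimate by several points.

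The SAP makes this harder to resolve. It never says whether a withdrawn subject who is not yet a case is missing or a non-case. Two programmers could therefore report different primary ARs from the same data, each pointing to a sentence in the plan.

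**Working it through.** **The plan's own figure.** Protocol 9.3.2 gives an exact 95% CI of 31.3% to 68.7% for 15 events in 30. The Clopper-Pearson method returns 31.30% to 68.70%, so it is used below. The documents give no figure for the effect of the withdrawal rule.

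**Inputs.** x = cases, n = subjects challenged, w = withdrawals not yet cases. No post-challenge withdrawal rate is stated. The only allowance, two per cohort in protocol 9.3.2, is for withdrawals before challenge. All values of w below are therefore assumptions.

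**Step 1: the rule against counting withdrawals as non-cases.** The protocol gives x/(n−w); the alternative is x/n. Since n−w ≤ n, the protocol figure is never the lower one.

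| x, n, w | Kept as non-cases, x/n | Excluded, x/(n−w) |
|---|---|---|
| 21, 30, 2 | 70.0% (50.6 to 85.3) | 21/28 = 75.0% (55.1 to 89.3) |
| 15, 30, 3 | 50.0% (31.3 to 68.7) | 15/27 = 55.6% (35.3 to 74.5) |
| 9, 12, 1 | 75.0% (42.8 to 94.5) | 9/11 = 81.8% (48.2 to 97.7) |
| 8, 12, 1 | 66.7% (34.9 to 90.1) | 8/11 = 72.7% (39.0 to 94.0) |

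One exclusion in a group of 12 adds 6 to 7 points in these examples.

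**Step 2: the rule against the true AR, withdrawal unrelated to outcome.** Let p = true AR, d = share withdrawing, f = share of the eventual cases among them who already met the definition (d and f assumed).

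- Protocol rule: [(1−d)p + dfp] / [(1−d) + dfp].
- All challenged subjects in the denominator: (1−d)p + dfp.
- All early withdrawals dropped, whatever their status: p.

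With p = 0.70 and f = 0.5:

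- d = 10%: protocol rule (0.630 + 0.035)/(0.900 + 0.035) = 0.665/0.935 = 71.1%; full denominator 66.5%.
- d = 20%: protocol rule (0.560 + 0.070)/(0.800 + 0.070) = 0.630/0.870 = 72.4%; full denominator 63.0%.
- f = 0: protocol rule 70.0%, no bias.

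**Step 3: withdrawal related to outcome.** Take 10 subjects, of whom 2 leave before meeting the definition and 6 of the other 8 are cases. The rule gives 6/8 = 75%. If both leavers would have become cases, the truth is 8/10 = 80% and the rule is too low. If neither would have, the truth is 6/10 = 60% and the rule is too high.

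**Step 4: the existing safeguard.** The Per-Protocol population drops every subject who withdraws before the end of the challenge period, whatever the case status. Protocol 9.5.2 uses it only when 10% or more of the analysis data would be lost, and SAP section 7 makes it optional even then. Counted by subject within a group, 1/12 = 8.3% and 2/30 = 6.7% both fall below that trigger.

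**The case against.** The strongest reply is that the effect is likely to be small and the obvious alternative may be worse. Subjects are confined inpatients, post-challenge withdrawal is strongly discouraged, and SAP 5.5 expects little missing data. Where withdrawal is unrelated to outcome, the protocol rule errs by +1.1 and +2.4 points in Step 2, while the full denominator errs by −3.5 and −7.0. This stands. It rules out prescribing the full denominator as if it were free of bias, and it limits the size of the point. It does not make an outcome-dependent denominator a sound rule.

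A reader might also infer four stronger things that the documents do not support.

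- **That Table 14 contradicts the protocol.** Its N is the Safety population, and Table 36, unlike Table 14, is explicitly limited to subjects followed for the whole challenge period. That favours a full denominator. But SAP 5.1 bases percentages on non-missing data and lets the printed N include missing observations, so Table 14 fits either reading. Nor does the change of label from ITT to Safety create a conflict, because the protocol defines both as everyone challenged.
- **That the rule can only inflate the AR.** This is true against counting withdrawals as non-cases. Step 3 shows that it is not true against the true AR.
- **That it would tip an escalation decision**, as 9/12 to 9/11 crosses 80%. The 80% and 70% cut-offs govern the interim AR; the exclusion sits in the final-analysis section, and neither document applies it at the interim. SAP 4.1 describes the interim AR across all cohort participants, sham included, a target of 13. On that base 9/13 = 69.2% becomes 9/12 = 75.0%, with no crossing. Other counts could cross (10/13 = 76.9% to 10/12 = 83.3%), but only if the rule were used there.
- **That subjects who feel well are the ones who leave.** Nothing in the documents says so.

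**Conclusion.** The point holds as a flaw in a stated rule that the SAP has left unreconciled. Followed as written, protocol 9.5.2 makes the primary denominator depend on case status. Relative to treating the same withdrawals as non-cases, the AR is equal or higher: 5 points in the 21-of-30 example with two withdrawals. Relative to the truth, the bias is about 1 point upward at 10% non-informative withdrawal, zero if no withdrawal had yet become a case, and of either sign if withdrawal is informative. These sizes rest on assumed withdrawal numbers. If nobody withdrew after challenge, the result does not change.

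It is still worth correcting, because the AR selects the dose, the groups are small, and the only planned analysis that ignores case status is conditional in the protocol and optional in the SAP.

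**What to change.** 1. In SAP 7.1.1 and the Table 14 footnote, replace the protocol 9.5.2 exclusion with one denominator rule that does not depend on case status, and say whether a withdrawn subject who is not yet a case is missing or a non-case. Two rules qualify: keep everyone challenged, or drop every early withdrawal. If the first is chosen, state its downward bias (66.5% against a true 70% in the Step 2 example at 10% withdrawal). If the second, state that it assumes withdrawal is unrelated to outcome.
2. State the denominator rule for the interim AR as well.
3. Whenever anyone withdraws after challenge, add to Table 14:
   - a bounds row counting all withdrawn not-yet-cases as non-cases, then all as cases (21 cases among 30 with two such withdrawals: 21/30 = 70.0% to 23/30 = 76.7%);
   - an evaluable row that excludes all early withdrawals whatever their case status, without the 10% Per-Protocol trigger.
4. Record the departure from protocol 9.5.2 in SAP section 14.

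The cost is a few sentences and one or two table rows. The reported AR may be slightly lower, or be shown with a wider range.

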#### 9.5.3 Analysis of the Secondary Endpoints

# 9.5.3.1 Analysis of Secondary Endpoints

Assessing the safety profile of the challenge virus is a secondary objective of the study. This will be measured by the number of adverse events reported and the percentage of subjects reporting adverse events through Day 29, and the number of serious adverse events and the percentage of subjects reporting adverse events through Day 57.

Influenza signs and symptoms and clinical lab findings determined to have exceeded the expected severity will be considered unsolicited adverse events. Events that are not consistent with illness due to influenza and abnormal vital signs will be considered unsolicited AEs as well. Solicited signs and symptoms of influenza as described in Section 4.1 will not be considered AEs. The severity (mild, moderate, or severe) of abnormal vital signs and clinical laboratory values will be presented according to the toxicity grading scales in Appendices A, B and C. Other events will be reported according to the criteria in Section 8.3.2.1. Relationship with receipt of the challenge virus will be assessed as described in Section 8.3.2.2.

The frequencies of AEs through Day 29 and SAEs through Day 57 will be presented by MedDRA® system organ class (SOC) and preferred term (PT), severity, relationship to challenge virus, challenge dose group, and across all subjects receiving active virus. Incidence will be assessed by the number and percentage of subjects in each challenge dose group ever reporting an event, along with associated 95% CI for the probability of the event. To further assess the safety of the challenge virus, the incidence of any related moderate or severe AE and any SAE will be calculated for each challenge dose group and compared as described in Section 9.5.1.

Adverse events and clinical laboratory results will be presented in data listings. Analyses of safety endpoints will be performed for the Safety population.

#### 9.5.3.2 Analysis of Secondary Immunological Endpoints

Secondary immunological objectives include describing the host serum antibody (HAI and MN) responses and anti-HA-stalk antibody responses at baseline and post-challenge.

For these titer data, GMTs and the proportions of subjects achieving seroconversion, defined as a minimum 4-fold rise in titer post-challenge, will be presented by challenge dose group and visit. Geometric mean fold-rise (GMFR) for anti-HA-stalk antibody titers will be included for post-challenge visits as well. Confidence intervals corresponding to these statistics will be computed for each group and visit as well. Hypothesis testing may be performed for select immunological endpoints and time points, which will be pre-specified in the SAP.

#### 9.5.4 Analysis of Exploratory Endpoints

Exploratory objectives for this study include further characterizing the immunological responses, assessing the impact of genetic variability on the immune, clinical, and viral responses, and further examining the clinical and physiological responses post-challenge.

# 9.5.4.1 Exploratory Immunological Endpoints

For analysis of exploratory immunological endpoints, immune responses will be described by visit and challenge dose group. For antibody titer data, geometric means will be computed for each group at each time point (GMTs), and seroconversion and geometric mean fold-rise (GMFR) at post-baseline visits will be calculated as well, where applicable. Confidence intervals corresponding to these statistics will be computed for each group as well, but formal hypothesis testing is not planned for descriptive summaries of exploratory endpoints.

Additional aggregate (i.e., encompassing data across multiple visits) immunological endpoints may include the duration of response, the timing and magnitude of the peak response, and the total immune response as measured by the area under the curve (where the study day is on the x-axis and the immune response is on the y-axis).

Neuraminidase inhibition antibody (NAI) responses will be analyzed similarly to HAI and MN assays, as described in 9.5.3.2. Other immunological endpoints will include frequencies of cell subsets, which will be described by mean frequencies within each group and the associated 95% CIs. Further details for data types not covered here will be given in the standalone SAP.

Exploratory immunological endpoints will be analyzed for the ITT population, with the PP population used for sensitivity analysis if at least 10% of analysis data would be excluded for the reasons described in Section 9.4. Subjects who withdraw prior to being evaluable for certain endpoints may be excluded from specific analyses in the ITT population, but all available data will be included in descriptive analyses.

# 9.5.4.2 Exploratory Genomic Endpoint

The frequencies of HLA class I and II alleles at baseline will be tabulated by challenge dose group and overall. The ability of pre-challenge HLA class I and II alleles to modulate the magnitude (as measured by serological conversion defined as a minimum 4-fold rise in post-challenge) of the immune response will be assessed using a two-sided Fisher's exact test. The relationship between HLA alleles and pre-existing immune status (baseline HAI, NAI, MN titer) will be evaluated via one-way ANOVA. The association between HLA class I and II alleles and peak shedding and total viral shedding for quantitative RT-PCR and quantitative culture will be assessed using a two-sided Wilcoxon Rank-Sum test. Depending on the number of observed alleles, multiple testing adjustment may be carried out using the Benjamini Hochberg procedure[10].

# 9.5.4.3 Exploratory Transcriptomic Endpoint

For the transcriptomics exploratory analysis, RNA sequencing data will be pre-processed by removing adapters and low-quality reads and mapping sequences to the latest human reference genome using splice-aware alignment software such as *HISAT2*. Gene expression quantification will be carried out by using the *Subread* software using the latest Ensembl [11] gene model annotations as a reference. Systematic differences in sequence coverage between samples will be accounted for using the TMM method [12] as implemented in the *edgeR* [13] R package. Principal component analysis, non-metric multidimensional scaling, and hierarchical clustering

analysis will be used to identify potential global outliers and systematic batch effect. Negative binomial models as implemented in *edgeR* [13] will be used to identify genes for each post-challenge day that were differentially expressed (DE) compared to pre-challenge. To control for testing multiple genes, the false-discovery rate (FDR) based on the Benjamini-Hochberg procedure[10] as implemented in the *p.adjust* R function will be applied. Genes with a FDR-adjusted p-value < 0.05 will be deemed to be significantly DE. The *pvclust* [14] R package will be applied to identify co-expressed DE gene clusters and cluster time trends will be visualized. Pathway enrichment analysis based on the latest MSigDB [15] and KEGG [16] databases as well as Blood Transcription Modules [17] accounting for gene length bias will be carried out using the implementation provided by the *goseq* [18] R package. Pathway maps color-coded by challenge effect will be provided for significantly enriched KEGG pathways. In addition, for each enriched pathway, time trends of the median of the average pathway response will be visualized. Additional details/analyses will be described in the SAP.

